**SAE reports and any other relevant safety information are to be forwarded to the Merck Global Safety [contact]**

A copy of all 15 Day Reports and Annual Progress Reports is submitted as required by FDA, European Union (EU), Pharmaceutical and Medical Devices agency (PMDA) or other local regulators. Investigators will cross reference this submission according to local regulations to the Merck Investigational Compound Number (IND, CSA, etc.) at the time of submission. Additionally investigators will submit a copy of these reports to Merck & Co., Inc. (Attn: Worldwide Product Safety; [contact]) at the time of submission to FDA.

#### **6.2.3.2 Events of Clinical Interest**

Selected non-serious and serious adverse events are also known as Events of Clinical Interest (ECI) and must be reported within 2 working days to Merck Global Safety. (Attn: Worldwide Product Safety; [contact]).

For the time period beginning when the consent form is signed until treatment allocation, any ECI, or follow up to an ECI, that occurs to any participant must be reported within 2 working days to Merck Global Safety if it causes the participant to be excluded from the trial, or is the result of a protocol-specified intervention, including but not limited to washout or discontinuation of usual therapy, diet, placebo treatment or a procedure.

For the time period beginning at treatment allocation through 90 days following cessation of treatment, or 30 days following cessation of treatment if the participant initiates new anticancer therapy, whichever is earlier, any ECI, or follow up to an ECI, whether or not related to Merck product, must be reported within 2 working days to Merck Global Safety.

Events of clinical interest for this trial include:

1. An overdose of Merck product, as defined in Section 7.2.1 - Definition of an Overdose for This Protocol and Reporting of Overdose to the Sponsor, that is not associated with clinical symptoms or abnormal laboratory results.

2. an elevated AST or ALT lab value that is greater than or equal to 3X the upper limit of normal and an elevated total bilirubin lab value that is greater than or equal to 2X the upper limit of normal and, at the same time, an alkaline phosphatase lab value that is less than 2X the upper limit of normal, as determined by way of protocol-specified laboratory testing or unscheduled laboratory testing.\*

**\*Note:** These criteria are based upon available regulatory guidance documents. The purpose of the criteria is to specify a threshold of abnormal hepatic tests that may require an additional evaluation for an underlying etiology.

#### **6.2.4 Evaluating Adverse Events**

An investigator who is a qualified physician will evaluate all adverse events according to the NCI Common Terminology for Adverse Events (CTCAE), version 4.0. Any adverse event which changes CTCAE grade over the course of a given episode will have each change of grade recorded on the adverse event case report forms/worksheets.

All adverse events regardless of CTCAE grade must also be evaluated for seriousness.

Table 7 Evaluating Adverse Events

An investigator who is a qualified physician, will evaluate all adverse events as to:

V4.0 CTCAE Grading	Grade 1	Mild; asymptomatic or mild symptoms; clinical or diagnostic observations only; intervention not indicated.
	Grade 2	Moderate; minimal, local or noninvasive intervention indicated; limiting age-appropriate instrumental ADL.
	Grade 3	Severe or medically significant but not immediately life-threatening; hospitalization or prolongation of hospitalization indicated; disabling; limiting self-care ADL.
	Grade 4	Life threatening consequences; urgent intervention indicated.
	Grade 5	Death related to AE
Seriousness	A serious adverse event is any adverse event occurring at any dose or during any use of Merck product that:	
	† Results in death ; or	
	† Is life threatening ; or places the participant, in the view of the investigator, at immediate risk of death from the event as it occurred (Note: This does not include an adverse event that, had it occurred in a more severe form, might have caused death.); or	
	† Results in a persistent or significant disability/incapacity (substantial disruption of one's ability to conduct normal life functions); or	
	† Results in or prolongs an existing inpatient hospitalization (hospitalization is defined as an inpatient admission, regardless of length of stay, even if the hospitalization is a precautionary measure for continued observation. (Note: Hospitalization for an elective procedure to treat a pre-existing condition that has not worsened is not a serious adverse event. A pre-existing condition is a clinical condition that is diagnosed prior to the use of a Merck product and is documented in the patient's medical history.); or	
	† Is a congenital anomaly/birth defect (in offspring of participant taking the product regardless of time to diagnosis); or	
	Is a new cancer (that is not a condition of the study) (although not serious per ICH definition, is reportable to the Sponsor within 24 hours and to Merck within 2 working days to meet certain local requirements); or	
	Is an overdose (whether accidental or intentional). Any adverse event associated with an overdose is considered a serious adverse event for collection purposes. An overdose that is not associated with an adverse event is considered a non-serious event of clinical interest and must be reported within 24 hours to the Sponsor and to Merck within 2 working days..	

Other important medical events that may not result in death, not be life threatening, or not require hospitalization may be considered a serious adverse event when, based upon appropriate medical judgment, the event may jeopardize the participant and may require medical or surgical intervention to prevent one of the outcomes listed previously (designated above by a †).	
Duration	Record the start and stop dates of the adverse event. If less than 1 day, indicate the appropriate length of time and units
Action taken	Did the adverse event cause Merck product to be discontinued?
Relationship to Merck Product	Did Merck product cause the adverse event? The determination of the likelihood that Merck product caused the adverse event will be provided by an investigator who is a qualified physician. The investigator's signed/dated initials on the source document or worksheet that supports the causality noted on the AE form, ensures that a medically qualified assessment of causality was done. This initialed document must be retained for the required regulatory time frame. The criteria below are intended as reference guidelines to assist the investigator in assessing the likelihood of a relationship between the test drug and the adverse event based upon the available information.  The following components are to be used to assess the relationship between Merck product and the AE; the greater the correlation with the components and their respective elements (in number and/or intensity), the more likely Merck product caused the adverse event (AE):  Exposure Is there evidence that the participant was actually exposed to Merck product such as: reliable history, acceptable compliance assessment (pill count, diary, etc.), expected pharmacologic effect, or measurement of drug/metabolite in bodily specimen?  Time Course Did the AE follow in a reasonable temporal sequence from administration of Merck product? Is the time of onset of the AE compatible with a drug-induced effect (applies to trials with investigational medicinal product)?  Likely Cause Is the AE not reasonably explained by another etiology such as underlying disease, other drug(s)/vaccine(s), or other host or environmental factors

Relationship to Merck Product (continued)		The following components are to be used to assess the relationship between the test drug and the AE: (continued)	
	Dechallenge	
Was Merck product discontinued or dose/exposure/frequency reduced?
 
If yes, did the AE resolve or improve?
 
If yes, this is a positive dechallenge. If no, this is a negative dechallenge.
 
(Note: This criterion is not applicable if: (1) the AE resulted in death or permanent disability; (2) the AE resolved/improved despite continuation of the Sponsor's product; or (3) the trial is a single-dose drug trial); or (4) Sponsor's product(s) is/are only used one time.)
	
	Rechallenge	
Was the participant re-exposed to Merck product in this study?
 
If yes, did the AE recur or worsen?
 
If yes, this is a positive rechallenge. If no, this is a negative rechallenge.
 
(Note: This criterion is not applicable if: (1) the initial AE resulted in death or permanent disability, or (2) the trial is a single-dose drug trial); or (3) Sponsor's product(s) is/are used only one time).
 
NOTE: IF A RECHALLENGE IS PLANNED FOR AN ADVERSE EVENT WHICH WAS SERIOUS AND WHICH MAY HAVE BEEN CAUSED BY MERCK PRODUCT, OR IF REEXPOSURE TO MERCK PRODUCT POSES ADDITIONAL POTENTIAL SIGNIFICANT RISK TO THE PARTICIPANT, THEN THE RECHALLENGE MUST BE APPROVED IN ADVANCE BY THE SPONSOR AS PER DOSE MODIFICATION GUIDELINES IN THE PROTOCOL.
	
	Consistency with Trial Treatment Profile	Is the clinical/pathological presentation of the AE consistent with previous knowledge regarding Merck product or drug class pharmacology or toxicology?	
The assessment of relationship will be reported on the case report forms /worksheets by an investigator who is a qualified physician according to his/her best clinical judgment, including consideration of the above elements.			
Record one of the following		Use the following scale of criteria as guidance (not all criteria must be present to be indicative of Merck product relationship).	
Yes, there is a reasonable possibility of Merck product relationship.		There is evidence of exposure to Merck product. The temporal sequence of the AE onset relative to the administration of Merck product is reasonable. The AE is more likely explained by Merck product than by another cause.	
No, there is not a reasonable possibility of Merck product relationship		Participant did not receive the Merck product OR temporal sequence of the AE onset relative to administration of Merck product is not reasonable OR the AE is more likely explained by another cause than the Merck product. (Also entered for a participant with overdose without an associated AE.)	

### **6.2.5 Sponsor Responsibility for Reporting Adverse Events**

All Adverse Events will be reported to regulatory authorities, IRB/IECs and investigators in accordance with all applicable global laws and regulations.

## **7.0 STATISTICAL ANALYSIS PLAN**

### **7.1 Statistical Analysis Plan Summary**

Statistical Consideration:

Efficacy:

- 1) The primary endpoint is Pathological complete response ([pCR](#)) after 3 doses. Pathological complete response will also be estimated for all patients who receive at least 1 dose of pembrolizumab (intent to treat). Those who do not undergo surgical resection will be classified as non-pCR for the intention to treat analysis. We will estimate the pCR rate among the group of patients who receive at least 3 doses of pembrolizumab and undergo surgical resection (the primary endpoint). Assuming the pCR is 80%, with 20 patients, the 95% confidence interval is (0.56, 0.94).
  
- 2) Rate of organ sparing at 1 year (primary tumor control and no metastatic disease) will be assessed for all patients who receive at least 1 doses of neoadjuvant pembrolizumab for the intention to treat analysis. In addition we will estimate the organ sparing rate at 1 year among the group of patients who receive at least 3 doses of neoadjuvant pembrolizumab and do not undergo surgical resection. Assuming the organ sparing rate of 0.7, with 10 patients, the 95% confidence interval is (0.35, 0.93) .

Safety monitoring:

Toxicity will be monitored using the Bayesian approach of Thall, Simon, Estey (1995, 1996) and the extension by Thall and Sung (1998). Multc Lean Desktop (version 2.1) was used to generate the stopping boundaries and the OC tables for toxicity monitoring. Toxicity monitoring will be performed (n=35 patients) throughout the study. Unacceptable toxicities are defined as any Grade 3 or higher probably or definite treatment-related CTCAE toxicity that occurs during the first 6 months of therapy. Denote the probability of toxicity by PT. We assume as a priori,  $PT \sim \text{beta}(0.5, 1.5)$ . Our stopping rule is given by the following probability statement:

$$\Pr(PT > 0.25 | \text{data}) > 0.85.$$

That is, we will stop the trial for new patient enrollment if at any time during the study, we determine that there is more than 85% chance that the unacceptable toxicity rate is more than 25%. This toxicity monitoring rule will be applied after the first 5 patients have been enrolled and evaluated, and then will be monitored by cohort of 5. Stopping boundaries corresponding to this stopping rule are listed in Table 8.

Table 8. Early stopping boundaries for toxicity monitoring

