## 1.0 TRIAL SUMMARY

Abbreviated Title	Neoadjuvant Pembrolizumab for Patients with Mismatch Repair Deficient Locally Advanced Solid Cancers
Trial Phase	II
Clinical Indication	Treatment of MSI high locally advanced solid tumors in the neoadjuvant setting
Trial Type	Interventional
Type of control	None
Route of administration	Intravenous
Trial Blinding	Unblinded, open-label
Treatment Groups	All patients will receive pembrolizumab 200mg every 3 weeks
Number of trial participants	35 patients
Estimated enrollment period	We estimate that the trial will require approximately 17 months from the first patient enrolling until the final patient signs informed consent.
Estimated duration of trial	We estimate that the trial will require approximately 24 months to allow full accrual and at least the first 6 cycles of pembrolizumab.
Duration of Participation	Until disease progression, drug intolerance, or 24 months of pembrolizumab therapy.
Estimated average length of treatment per patient	One year

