#### **4.5 Participant Replacement Strategy**

A participant that discontinues from the study after receiving a dose of pembrolizumab will not be replaced. Clinical Criteria for Early Trial Termination

Early trial termination will be the result of the criteria specified below:

1. Quality or quantity of data recording is inaccurate or incomplete
2. Poor adherence to protocol and regulatory requirements
3. Incidence or severity of adverse drug reaction in this or other studies indicates a potential health hazard to participants
4. Plans to modify or discontinue the development of the study drug

In the event of Merck decision to no longer supply study drug, ample notification will be provided so that appropriate adjustments to participant treatment can be made.

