## 6.2 Assessing and Recording Adverse Events

An adverse event is defined as any untoward medical occurrence in a patient or clinical investigation participant administered a pharmaceutical product and which does not necessarily have to have a causal relationship with this treatment. An adverse event can therefore be any unfavorable and unintended sign (including an abnormal laboratory finding, for example), symptom, or disease temporally associated with the use of a medicinal product or protocol-specified procedure, whether or not considered related to the medicinal product or protocol-specified procedure. Any worsening (i.e., any clinically significant adverse change in frequency and/or intensity) of a preexisting condition that is temporally associated with the use of the Merck's product, is also an adverse event.

Changes resulting from normal growth and development that do not vary significantly in frequency or severity from expected levels are not to be considered adverse events. Examples of this may include, but are not limited to, teething, typical crying in infants and children and onset of menses or menopause occurring at a physiologically appropriate time.

Merck product includes any pharmaceutical product, biological product, device, diagnostic agent or protocol-specified procedure, whether investigational (including placebo or active comparator medication) or marketed, manufactured by, licensed by, provided by or distributed by Merck for human use.

Adverse events may occur during the course of the use of Merck product in clinical trials, or as prescribed in clinical practice, from overdose (whether accidental or intentional), from abuse and from withdrawal.

All AEs, SAEs and other reportable safety events that occur after the consent form is signed but before treatment allocation must be reported by the investigator if the participant is receiving placebo run-in or other run-in treatment, if the event cause the participant to be excluded from the study, or is the result of a protocol-specified intervention, including but not limited to washout or discontinuation of usual therapy, diet, or a procedure.

- All AEs from the time of treatment allocation through 30 days following cessation of study treatment must be reported by the investigator.

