# of patients (in cohort size of 5, starting from the 5th patient)      Stop this cohort if there are this many patients with toxicities:

# of patients ( in cohort size of 5, starting from the 5 th patient)	Stop this cohort if there are this many patients with toxicities:
5	3-5
10	5-10
15	6-15
20	8-20
25	9-25
30	11-30
35	Always stop with this many patients

Table 9. Operating characteristic for toxicity monitoring

True toxicity rate	Prob(stop the trial early)	Average number of patients treated
0.15	0.04	33.87
0.25	0.27	29.02
0.35	0.66	20.46
0.45	0.93	12.94

If patients do not respond to pembrolizumab, they would stop the treatment after two doses. In case the patients have resectable tumors, the subsequent surgical resection will be monitored. Patients will be allowed up to 6 months to have surgery. We expect that 80% of these patients with resectable tumors would undergo surgery. After 5 patients falling into this category, the

Bayesian stopping rule:  $\text{Pr}(\text{surgery rate} > 0.8 | \text{data}) < 0.01$  will be continuously implemented assuming the surgery rate follows a Beta prior (0.8,0.2). That is, if at any time after enrolling 5 patients who have resectable tumor and don't respond to pembrolizumab, we determine that there is a less than 1% chance that the surgery rate is more than 80%, we will stop enrollment of the study. Assuming there are 20 patients, the surgery rate monitoring rule will be applied after the first 5 patients have been enrolled and evaluated, and then will be monitored by cohort of 5. Stopping boundaries corresponding to this stopping rule are listed in Table 10 (operating characteristic in table 11). For example, if there is none or only 1 patient out of the 1st 5 patients undergo surgery, the study will be stopped. Table 10. Early stopping boundaries for surgery rate monitoring for patients who do not respond to pembrolizumab but with resectable tumor

# of patients ( in cohort size of 5, starting from the 5 th patient)	Stop the study if there are this many patients with surgery
5	0-1
10	0-4
15	0-7
20	0-11

Table 11. Operating characteristic for surgery rate monitoring for patients who do not respond to pembrolizumab but with resectable tumor

True surgery rate	Prob(stop the trial early)
0.5	0.56
0.6	0.27
0.7	0.08
0.8	0.01

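### Table 9's average number treated assumes that nobody enters while a cohort is evaluated; under the planned accrual it may be right or 8 to 11 patients too low, depending on which of two triggers is meant

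*Combined protocol and SAP*

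**What the plan says.** Section 7.1 (Safety monitoring) defines the event as a Grade 3 or higher, probably or definitely treatment-related "CTCAE toxicity that occurs during the first 6 months of therapy". The prior is Beta(0.5, 1.5), and the criterion is a posterior probability above 0.85 that the rate exceeds 0.25.

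Two consecutive sentences say when the rule acts:
- Running trigger: "we will stop the trial for new patient enrollment if at any time during the study" the criterion is met.
- Cohort trigger: "This toxicity monitoring rule will be applied after the first 5 patients have been enrolled and evaluated", and then by cohorts of 5.

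Table 8 gives boundaries at 5, 10, 15, 20, 25 and 30 patients. Table 9 gives the probability of stopping early and the "Average number of patients treated" at four true rates.

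On timing, Section 1.0 states: "We estimate that the trial will require approximately 17 months from the first patient enrolling until the final patient signs informed consent". It puts the whole trial at about 24 months. No section states that enrolment is held while a cohort is evaluated.

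Two provisions bear on when a patient counts as evaluated. Section 7.1, after Table 9, says: "If patients do not respond to pembrolizumab, they would stop the treatment after two doses". Section 6.2 says: "All AEs from the time of treatment allocation through 30 days following cessation of study treatment must be reported by the investigator"; serious events are collected for longer.

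**The concern.** Table 9 is the plan's numerical evidence that the rule limits exposure if the toxicity rate is too high. An average of 12.94 treated at a rate of 0.45 tells the reader that a badly toxic regimen would be stopped after roughly 13 patients. With a 6-month window and about two entries a month, some 12 further patients can start treatment between the entry of a cohort's last patient and the end of that patient's evaluation. Table 9 counts none of them.

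The plan also leaves open how an event-free patient still inside the 6 months counts at a look, and when a patient who leaves after two doses counts as evaluated. The second matters because collection of non-serious events ends 30 days after that patient stops.

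**Working it through.** **Inputs.** From Section 7.1: the prior, the criterion, the 6-month window, and looks at 5 to 30 of at most 35 patients. From Section 1.0: 35 patients over about 17 months. With even entry (assumed), patient i enters at (i − 1) × 17/34 = (i − 1) × 0.5 months.

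**Reproducing Tables 8 and 9.** After x toxicities in n patients the posterior is Beta(0.5 + x, 1.5 + n − x). The smallest x with Pr(rate > 0.25) > 0.85 is 3/5, 5/10, 6/15, 8/20, 9/25 and 11/30, as in Table 8. Let s(n) be the exact probability of first crossing at look n.

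| Look n | 5 | 10 | 15 | 20 | 25 | 30 |
|---|---|---|---|---|---|---|
| s(n), rate 0.35 | 0.2352 | 0.0966 | 0.1645 | 0.0490 | 0.0899 | 0.0290 |
| s(n), rate 0.45 | 0.4069 | 0.1650 | 0.2033 | 0.0552 | 0.0730 | 0.0215 |

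Average N = Σ n·s(n) + 35·(1 − Σ s(n)). At 0.15/0.25/0.35/0.45 this gives 33.87/29.02/20.46/12.94, with crossing probabilities 0.044/0.269/0.664/0.925. These are Table 9's values, so Table 9 counts exactly n patients treated at look n.

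**Could accrual be held?** A hold at each look replaces a 0.5-month gap by 6 months: 17 + 6 × (6 − 0.5) = 50 months of enrolment, against about 17 planned.

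**(A) Cohort trigger, enrolment open.** The look at n falls at (n − 1) × 0.5 + 6 months: 8.0, 10.5, 13.0, 15.5, 18.0 and 20.5. By then min(35, n + 12) patients have entered: 17, 22, 27, 32, 35 and 35. Replacing n by these counts:

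- Rate 0.35: 17(0.2352) + 22(0.0966) + 27(0.1645) + 32(0.0490) + 35(1 − 0.5453) = 28.05 (28.047 before rounding).
- Rate 0.45: 17(0.4069) + 22(0.1650) + 27(0.2033) + 32(0.0552) + 35(1 − 0.8304) = 23.74.
- Rates 0.15 and 0.25: 34.39 and 32.10.

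The excess is 28.05 − 20.46 = 7.59 and 23.74 − 12.94 = 10.80 patients. That implies 7.59 × 0.35 = 2.7 and 10.80 × 0.45 = 4.9 more patients with an unacceptable toxicity. The looks at 25 and 30 come after the last entry at month 17, so the chance of stopping while enrolment is open is the sum of the first four s(n): 0.55 and 0.83.

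Variants of (A) at 0.35/0.45:

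| Assumption | Average treated |
|---|---|
| Random (Poisson) entry | 28.0–28.2 / 23.6–24.0 |
| Accrual over 24 months | 25.7 / 20.3 |
| Half the patients stop after dose 2 (day 21) and are evaluated to day 21 + 30 = 51 | 27.4 / 22.8 |
| As above, and a patient with an event counts as evaluated at the event (uniform onset) | 26.3 / 21.0 |
| All patients evaluated at day 51 | 22.5 / 15.7 |

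**(B) Running trigger.** This was simulated with the same accrual. All onset curves are assumptions: Section 4.2.2 says only that immune-related events may come early or late. The first column acts as soon as a Table 8 count is reached among the first n patients. The second applies the posterior criterion at every n from 5.

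| Assumed onset | Table 8 counts, 0.35/0.45 | Every n from 5, 0.35/0.45 |
|---|---|---|
| Within 1 month | 20.2 / 12.5 | 17.4 / 10.6 |
| Within 6 weeks | 20.5 / 12.9 | not tabulated |
| Within 3 months | 21.8 / 14.7 | 19.3 / 12.7 |
| Front-loaded over 6 months | 22.0 / 14.9 | 19.4 / 12.9 |
| Uniform over 6 months | 24.4 / 18.2 | 22.0 / 16.2 |
| Late in the 6 months | 25.8 / 20.4 | 23.7 / 18.5 |

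If action also waits for the nth patient to enter, the first column runs from about 20.6/13.1 to 25.9/20.4. Checking at every n raises the chance of stopping at the 0.25 limit from 0.27 to 0.36 (exact, no lag), so it is a different rule from the one in Table 9.

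**The case against.** The strongest reply is that (A) strains the text. Under it, a third toxicity among the first five patients, seen in month 1, would prompt nothing until month 8. Yet Section 7.1 provides for stopping whenever the criterion is met. The trial is single-centre (Section 2.1), adverse events are reviewed every cycle (Section 5.1), and serious events reach the sponsor within 24 hours (Section 6.2.3.1). On the running trigger with early onset, Table 9 is met or bettered. This stands, and it makes (A) the upper end of the range. It does not rescue Table 9 as written, because the next sentence ties the rule to evaluated cohorts and no onset assumption is stated.

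The inputs are also soft. The 17 months is an estimate, and the finding that the look at 25 comes too late rests on one month (18.0 against 17). With 24-month accrual that look falls at 24 × 24/34 + 6 = 22.9 months, before the last entry. Early leavers shorten evaluation by an unknown amount.

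Other safeguards exist. Section 4.5 allows termination if "Incidence or severity of adverse drug reaction in this or other studies indicates a potential health hazard to participants", Table 3 governs individual toxicities, and enrolment is capped at 35. But Section 4.5 has no numerical trigger, and none of these corrects Table 9.

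A reader might infer that Table 9 understates exposure on every reading, or that the stopping rule itself is wrong. The documents support neither: the running trigger can give no excess, and Table 8 and the crossing probabilities are correct.

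**Conclusion.** The point holds as a conditional one. Table 9's average number treated rests on an unstated condition that the planned accrual does not meet, and the excess depends on which trigger is meant. It ranges from none, or a small shortfall (about 3 patients at 0.35 if the criterion is checked at every n and onset is within a month), up to 7.6 patients at 0.35 and 10.8 at 0.45. The upper end assumes even accrual over 17 months, no hold, and a full 6-month wait at each look. At 0.25 the upper end is 32.1 against 29.0. At 0.15 the gap is negligible under (A) and under (B) at the Table 8 counts (33.9 to 34.4 against 33.9).

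The probability of ever crossing stays 0.66/0.93. What changes is whether crossing can still prevent an entry. Severity is minor to moderate: the arithmetic is certain, but the size depends on a reading and an onset pattern that the documents do not fix.

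**What to change.** 1. Reconcile the two trigger sentences in Section 7.1 so that one trigger is defined, and say whether it applies only at the Table 8 counts or at every n.
2. Reissue Table 9 by simulation for that trigger, with 35 patients in about 17 months, the 6-month window and a stated range of onset timings. Put the accrual assumption beside the table, and say whether stopping early means stopping while enrolment is open.
3. State that an event-free patient with under 6 months of follow-up is pending, not toxicity-free, and say when a patient who stops after two doses counts as evaluated.

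The prior, threshold and Table 8 boundaries need no change if looks stay at the Table 8 counts. The cost is a short simulation and a few lines of text, with no added patients. The stated figures will probably look somewhat less favourable. If the running trigger is kept, toxicity counts must be reviewed as events occur and not only at cohort looks.
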